1. TITLE OF THE STUDY

A phase II study of durvalumab (MEDI4736) in patients with mismatch repair deficient or *POLE* mutated metastatic colorectal cancer

3. INTRODUCTION AND STUDY RATIONALE

3.1. INTRODUCTION

Recent advances have made survival advances of patients with metastatic colorectal cancer (mCRC) upto median 30 months after upfront targeted agents plus doublet chemotherapy (Figure 1).^{1,2}

Figure 1. Survival advances of metastatic colorectal cancer patients after optimized first-line systemic chemotherapy.

	Overall survival		Progression-free survival	
	Bevacizumab + chemotherapy	Cetuximab + chemotherapy	Bevacizumab + chemotherapy	Cetuximab + chemotherapy
FIRE-3	25.0	28.7	10.3	10.0
	HR 0.77, p = 0.017		HR 1.06, p = 0.547	
CALGB 80405	29.0	29.9	10.8	10.4
	HR 0.925, p = 0.34		HR 1.04, p = 0.55	

Later-line treatments after failure to standard treatments, however, are limited; regorafenib and TAS-102 showed mild improvement of survival without significant response rates although those agents had rather higher frequencies of significant adverse events (Figure 2).³⁻⁵

Figure 2. Limited survival advantages in the later-line setting; roughly 2 months of overall survival benefit with higher cost and higher frequencies of adverse events.

	OS <small>primary endpoint</small>		PFS	
	Experimental	Placebo	Experimental	Placebo
CORRECT <small>Regorafenib</small>	6.4	5.0	1.9	1.7
	HR 0.77, p = 0.0052		HR 0.49, p < 0.0001	
CONCUR <small>Regorafenib in ASIAN</small>	8.8	6.3	3.2	1.7
	HR 0.55, p = 0.00016		HR 0.31, p < 0.0001	
RECOURSE <small>TAS-102</small>	7.1	5.3	2.0	1.7
	HR 0.68, p < 0.001		HR 0.48, p < 0.001	

Mismatch repair (MMR) deficiency or microsatellite instability-high (MSI-H) itself is better prognostic factor in the resected stage II or III colorectal cancer; however, they played a

role of negative predictive factor for adjuvant fluorouracil-based chemotherapy in patients with resected colorectal cancer.⁶⁻⁸ In the adjuvant setting, fluoropyrimidine based adjuvant chemotherapy did not benefit or did even harm for patient with resected stage II colorectal cancer with MSI-H or MMR deficiency. Adjuvant fluoropyrimidines even did not any benefit in those with resected stage III colorectal cancer with MSI-H or MMR deficiency.

In the metastatic setting, MMR deficiency or MSI-H represented poor prognosis and predictive of poor treatment responses from systemic treatments.⁹ However, their positive predictive role has been documented from the results of the KEYNOTE-016 trial.¹⁰

CheckMate 142 is evaluating nivolumab (3 mg/kg) with and without ipilimumab (Yervoy; 1 mg/kg) in patients with metastatic MMR-deficient/MSI-H colorectal cancer. The objective response rate was 31.1%, and 68.9% of patients demonstrated disease control for at least 12 weeks. Responses occurred early, at a median of 2.8 months, and the median duration of response has not been reached.¹¹

The *POLE* gene encodes the catalytic subunit of DNA polymerase epsilon, and it involves DNA repair and chromosomal replication. The *POLE* mutations are located in the exonuclease domain, and their presence has already been reported in the various cancers including colorectal and endometrial cancer; however, its role as a prognostic or predictive factor has not been studied yet.¹²⁻¹⁴ Our recent study demonstrated that the *POLE* mutations were found in 6 out of 28 colorectal cancer patients, characterized as younger age (< 40 years) and mismatch repair proficient (or MSS) tumors. More interestingly, 6 patients harbouring *POLE* mutations had higher somatic mutation loads in their tumors (ranged 2000 to 12,000) by whole-exom sequencing, compared to 50 to 150 mutation loads in those without *POLE* mutations (Figure 4).¹⁵

Figure 4. POLE mutation represents higher somatic mutation loads (recent published internal data).

The *POLE* mutations represent high somatic mutation loads in patients with colorectal cancer, especially in those with MMR proficient or MSS (microsatellite stable), therefore, tumors harbouring *POLE* mutations might be susceptible to immune checkpoint blockade.

3.2. DURVALUMAB (MEDI4736)

Durvalumab is a selective, high-affinity human IgG1 monoclonal antibody that blocks PD-L1 binding to PD-1 and CD80 but does not bind to PD-L2, avoiding potential immune-related toxic effects due to PD-L2 inhibition, which has been noted in susceptible animal models.

Recent studies demonstrated that durvalumab is safe and active in patients with non-small cell lung cancer and bladder cancer.

For non-small cell lung cancer patients, 102 patients were enrolled into the dose-escalation phase and received durvalumab plus tremelimumab. The maximum tolerated dose was exceeded in the cohort receiving durvalumab 20 mg/kg every 4 weeks plus tremelimumab 3 mg/kg. The most frequent treatment-related grade 3 and 4 adverse events were diarrhoea (11%), colitis (9%), and increased lipase (8%). Evidence of clinical activity was noted both in patients with PD-L1-positive tumours and in those with PD-L1-negative tumours. Investigator-reported confirmed objective responses were achieved by six (23%, 95% CI 9-44) of 26 patients in the combined tremelimumab 1 mg/kg cohort, comprising two (22%, 95% CI 3-60) of nine patients with PD-L1-positive tumours and four (29%, 95% CI 8-58) of 14 patients with PD-L1-negative tumours, including those with no PD-L1

staining (four [40%, 95% CI 12-74] of ten patients).¹⁶

For bladder cancer patients, durvalumab 10 mg/kg every 2 weeks was administered intravenously for up to 12 months. The most common treatment-related adverse events (AEs) of any grade were fatigue (13.1%), diarrhea (9.8%), and decreased appetite (8.2%). Grade 3 treatment-related AEs occurred in three patients (4.9%); there were no treatment-related grade 4 or 5 AEs. The objective response rate was 31.0% (95% CI, 17.6 to 47.1) in 42 response-evaluable patients, 46.4% (95% CI, 27.5 to 66.1) in the PD-L1-positive subgroup, and 0% (95% CI, 0.0 to 23.2) in the PD-L1-negative subgroup. Durvalumab demonstrated a manageable safety profile and evidence of meaningful clinical activity in PD-L1-positive patients with bladder cancer, many of whom were heavily pretreated.¹⁷

At present, studies of durvalumab with or without other agents for various tumor types are still ongoing.¹⁸⁻²² Risks with durvalumab include, but are not limited to, diarrhoea/colitis, pneumonitis/interstitial lung disease (ILD), endocrinopathies (ie, events of hypophysitis/hypopituitarism, adrenal insufficiency, hyper- and hypothyroidism, type I diabetes mellitus (which may present with diabetic ketoacidosis), and diabetes insipidus), hepatitis/increases in transaminases, nephritis/increases in creatinine, rash/dermatitis (including pemphigoid), myocarditis, myositis/polymyositis, immune thrombocytopenia, infusion related reactions, hypersensitivity reactions, pancreatitis, encephalitis, serious infections, subcutaneous injection site reaction, and other rare or less frequent inflammatory events including neuromuscular toxicities (eg, Guillain-Barré syndrome, myasthenia gravis).

For information on all identified and potential risks with durvalumab please always refer to the current version of the durvalumab IB.

In monotherapy clinical studies, AEs at an incidence of $\geq 20\%$ include events such as fatigue and decreased appetite. Approximately 10% of participants discontinued the drug due to an AE.

Please see the current version of the IB for a detailed summary of the monotherapy data including AEs, serious adverse events (SAEs), and Common Terminology Criteria for Adverse Events (CTCAE) Grade 3 to 5 events reported across the durvalumab program.

3.3. FIXED DOSING

A population PK model was developed for durvalumab using monotherapy data from a Phase 1 study (*study 1108; N=292; doses= 0.1 to 10 mg/kg Q2W or 15 mg/kg Q3W; solid tumors*). Population PK analysis indicated only minor impact of body weight (WT) on PK of durvalumab (coefficient of ≤ 0.5). The impact of body WT-based (10 mg/kg Q2W) and

fixed dosing (750 mg Q2W) of durvalumab was evaluated by comparing predicted steady state PK concentrations (5th, median and 95th percentiles) using the population PK model. A fixed dose of 750 mg was selected to approximate 10 mg/kg (based on median body WT of ~75 kg). A total of 1000 patients were simulated using body WT distribution of 40–120 kg. Simulation results demonstrate that body WT-based and fixed dosing regimens yield similar median steady state PK concentrations with slightly less overall between-subject variability with fixed dosing regimen.

Similar findings have been reported by others.²⁴⁻²⁷ Wang and colleagues investigated 12 monoclonal antibodies and found that fixed and body size-based dosing perform similarly, with fixed dosing being better for 7 of 12 antibodies.²⁵ In addition, they investigated 18 therapeutic proteins and peptides and showed that fixed dosing performed better for 12 of 18 in terms of reducing the between-subject variability in pharmacokinetic/pharmacodynamics parameters.²⁶

A fixed dosing approach is preferred by the prescribing community due to ease of use and reduced dosing errors. Given expectation of similar pharmacokinetic exposure and variability, we considered it feasible to switch to fixed dosing regimens. Based on average body WT of 75 kg, a fixed dose of 1500 mg Q4W durvalumab (equivalent to 20 mg/kg Q4W) is included in the current study. Fixed dosing of durvalumab is recommended only for subjects with > 30kg body weight due to endotoxin exposure. Patients with a body weight less than or equal to 30 kg should be dosed using a weight-based dosing schedule (Appendix B).

3.4. RATIONALE OF THE STUDY

PD-1 blockade (pembrolizumab) demonstrated promising efficacy outcomes in patients with MMR deficient or MSI-H mCRC.¹⁰ Another immune check point blockade, targeting PD-L1 in these patients also demonstrated promising activity (nivolumab for MSI-H mCRC, CHECKMATE-142, NCT02060188); the confirmed response rate was 27% (9/33) without any significant adverse event.²⁸

Immunotherapy for this population is worthy of further investigation and in unmet needs both in terms of finding adequate agents and selecting adequate population. On the bases of these results, we planned this study of durvalumab monotherapy, another PD-L1 blockade, for MMR deficient or MSI-H or *POLE* mutated mCRC patients to evaluate the efficacy and safety.

4. STUDY OBJECTIVES

The objective of this study is to investigate the efficacy and safety of durvalumab in patients with mismatch repair deficient or microsatellite instable or *POLE* mutated metastatic colorectal cancer refractory to irinotecan, oxaliplatin and fluoropyrimidines.

4.1. PRIMARY OBJECTIVE

- Objective response rates (RECIST 1.1)

4.2. SECONDARY OBJECTIVES

- Response rates by irRECIST
- Disease control rates
- Progression-free survival
- Overall survival
- Safety and toxicity assessments
- Exploratory biomarker analysis
 - Opal Multiplex Tissue Staining with Opal™ including PD-1 and PD-L1

5. STUDY DESIGN

5.1. DESIGN OVERVIEW

This is a prospective, open-label, multicenter phase II study to investigate the efficacy and safety of durvalumab monotherapy.

A total of 33 patients who meet the eligible criteria will be accrued (17 for mismatch repair deficient or microsatellite instable colorectal cancer and 16 for *POLE* mutated colorectal cancer).

Study treatment will be continued until at least one of the following occurs;

- Progressive disease as defined by Response Evaluation Criteria In Solid Tumors (RECIST) version 1.1. or clinical progression by the decision of investigators; Treatment through progression is at the investigator's discretion, and the investigator should ensure that patients do not have any significant, unacceptable, or irreversible toxicities that indicate that continuing treatment will not further benefit the patient. The Investigator

should ensure that patients still meet all of the inclusion criteria and none of the exclusion criteria for this study.

- Death.
- Unacceptable adverse events.
- Withdrawal of consent or lost to follow-up.
- Adverse events that, in the opinion of the investigator or the sponsor, contraindicates further dosing.
- Subject is determined to have met one or more of the exclusion criteria for study participation at study entry and continuing investigational therapy might constitute a safety risk.
- Treating physician determines discontinuation of treatment is in the subject's best interest.
- Non-compliance to the study protocol.
- Pregnancy or intent to become pregnant.

5.2. JUSTIFICATION OF THE DESIGN

As described previously, limited drugs are available in patients with metastatic colorectal cancer who have failed after standard therapies. Later-line treatments of currents showed limited antitumor activity in this setting. Mismatch repair deficiency (microsatellite instability) and *POLE* mutation is proved to be a reasonable target for immunotherapy for colorectal cancer patients; therefore, durvalumab monotherapy in this setting could be a valid option.

6. STUDY POPULATION

6.1. ELIGIBILITY

6.1.1. INCLUSION CRITERIA

1. Histologically or cytologically confirmed adenocarcinoma of the colon or the rectum.
2. Mismatch repair deficient or microsatellite instable (defined below), or *POLE* mutated tumors
 - A. Mismatch repair deficient: loss of expression by immunohistochemical stains ≥ 1 out of 4 markers (MLH1, MSH2, MSH6, PMS2)
 - B. Microsatellite instable: loss of stability ≥ 2 out of 5 gene panels (BAT-25, BAT-26, D2S123, D5S346, D17S250)
 - C. *POLE* gene: P286R mutation or other mutation

3. Refractory to prior fluoropyrimidines, irinotecan and oxaliplatin (progressed during or within 6 months of those agents).
4. ≥ 1 measurable lesion(s) by RECIST 1.1.
5. Unresectable advanced or metastatic disease.
6. Age over 20 years old.
7. ECOG performance status of 0-1 or lower.
8. Adequate organ functions.
 - A. Bone marrow function: Hemoglobin ≥ 9.0 g/dL, ANC $\geq 1,500/\text{mm}^3$, platelet $\geq 100,000/\text{mm}^3$
 - B. Hepatic functions: bilirubin ≤ 1.5 X ULN, AST/ALT ≤ 2.5 X ULN (≤ 5 X ULN in cases of liver metastasis)
 - C. Renal functions: serum Cr ≤ 1.5 X ULN or calculated CCr (Cockcroft) > 40 ml/min
9. Be willing and able to comply with the protocol for the duration of the study.
10. Give written informed consent prior to study-specific screening procedures, with the understanding that the patient has the right to withdraw the study at any time, without prejudice.
11. Female subjects must either be of non-reproductive potential (≥ 60 years old and no menses for ≥ 1 year without an alternative medical cause, or history of hysterectomy, or history of bilateral tubal ligation, or history of bilateral oophorectomy) or must have a negative serum pregnancy test upon study entry.
12. Women of childbearing potential and men must agree to use adequate contraception since signing of the IC form until at least 90days after the last study drug administration.

6.1.2. EXCLUSION CRITERIA

All of the following exclusion criteria should be checked at the time of screening procedure.

1. Any prior treatment with PD-1 or PD-L1 inhibitor, including durvalumab.
2. Involvement in the planning and/or conduct of the study.
3. Receipt of the last dose of chemotherapy ≤ 28 days prior to the first dose of study drugs.
4. Mean QT interval corrected for heart rate (QTc) ≥ 470 msec calculated from 3 electrocardiograms (ECGs) using Frediricia's Correction.
5. Any unresolved toxicity NCI CTCAE Grade ≥ 2 from previous anticancer therapy with the exception of alopecia, vitiligo, and the laboratory values defined in the inclusion criteria
6. Patients with Grade ≥ 2 neuropathy will be evaluated on a case-by-case basis after consultation with the Study Physician.

7. Patients with irreversible toxicity not reasonably expected to be exacerbated by treatment with durvalumab may be included only after consultation with the Study Physician.
8. Any concurrent chemotherapy, IP, biologic, or hormonal therapy for cancer treatment. Concurrent use of hormonal therapy for non-cancer-related conditions (eg, hormone replacement therapy) is acceptable.
9. Current or prior use of immunosuppressive medication within 14 days before the first dose of durvalumab, with the exceptions of intranasal and inhaled corticosteroids or systemic corticosteroids at physiologic doses, which are not to exceed 10 mg/day of prednisolone, or an equivalent corticosteroid.
10. Concurrent or previous history of another primary cancer within 3 years prior to randomisation except for curatively treated cervical cancer in situ, non-melanomatous skin cancer, superficial bladder cancer (pTis and pT1) and curatively treated thyroid cancer of any stage. Concurrent, histologically confirmed, unresected thyroid cancer without distant metastasis could be allowed with the agreement of the chief principal investigator.
11. Uncontrolled CNS metastases; permitted if asymptomatic or neurologically stable.
12. Prior radiation therapy would be permitted, but non-irradiated evaluable lesions should be present at study entry.
13. Radiation therapy during study treatment is not permitted, but if the local investigator decides that radiation therapy should be given during study treatments, he should be convinced that there is no evidence of disease progression with agreement of the chief principal investigator.
14. Congestive heart failure \geq New York Heart Association (NYHA) class 2.
15. Unstable angina, new-onset angina within 3 months, or history of myocardial infarction within 6 months before the study entry.
16. Active or prior documented autoimmune disease within the past 2 years; subjects with vitiligo, Grave's disease, or psoriasis not requiring systemic treatment (within the past 2 years) are not excluded.
17. Active or prior documented inflammatory bowel disease.
18. History of prior immunodeficiency.
19. History of allogeneic organ transplantation.
20. History of hypersensitivity to durvalumab or any excipient.
21. Clinical diagnosis of active tuberculosis.
22. Receipt of live attenuated vaccination within 30 days prior to study entry.
23. Known history of testing positive for HIV
24. Hepatitis B virus (HBV) or hepatitis C virus (HCV) infection at screening (positive HBV surface antigen or HCV RNA if anti-HCV antibody screening test positive)
Except, resolved HBV infection (as evidenced by detectable HBV surface antibody,

detectable HBV core antibody, undetectable HBV DNA, and undetectable HBV surface antigen) or Chronic HBV infection (as evidenced by detectable HBV surface antigen or HBV DNA). Subjects with chronic HBV infection must have HBV DNA < 100 IU/mL and must be on antiviral therapy.

25. Major surgery or significant traumatic injury within 28 days prior to study treatment.
26. Non-healing wound, ulcer, or bone fracture.
27. Current evidence of significant gastrointestinal bleeding or (impending) obstruction.
28. Concomitant participation in another interventional clinical trial.
29. Pregnant or breast-feeding subjects. Women of child-bearing potential must have pregnancy test within 7 days and a negative result must be documented before start of study treatment.
30. Substance abuse, medical, psychological or social conditions that may interfere with the subject's participation in the study or evaluation of the study results.

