
제외 기준
	
1. 이전에 durvalumab을 포함한 PD-1 또는 PD-L1 억제제를 사용한 적이 있는 경우.
 
2. 연구 계획 또는 수행에 관계된 종사자
 
3. 마지막 화학요법 시행 후 28일이 지나지 않은 경우
 
4. QTc \geq 470 msec 이상인 경우 (3회의 EKG 시행 후 평균 값, Frediricia's Correction)
 
5. 이전 항암요법으로부터 해결되지 않은 CTCAE 2등급 이상인 독성 (탈모, 백반증, 선정기준에 적합하지 않은 실험실검사 결과 제외)
 
6. 2등급 이상의 신경병증 환자의 경우 대상자 질환에 대한 평가는 연구자의 의학적 자문 이후 진행한다.
 
7. 비가역성 독성 환자에서 durvalumab 치료가 증상을 더 악화하지 않을 경우에는 연구자의 의학적 판단을 기준으로 한다.
 
8. 항암 치료를 위해 화학요법, 시험약, 생물학적 제제, 또는 호르몬 요법을 현재 사용하는 환자. 암과 무관한 상태에 대한 호르몬 요법의 동시 사용(예: 호르몬 대체 요법)은 허용된다.
 
9. 14일 이내의 면역 억제제 사용, 단 흡입성 스테로이드나 생리적 용량의 스테로이드는 허용한다 (10 mg/day of prednisolone 또는 equivalent dose의 다른 스테로이드 제제).
 
10. 3년 이내에 다른 원발암의 병력이 있는 경우, 단 수술적으로 완치된 표재성 자궁 경부암, 표재성 피부암 (흑색종 제외), 표재성 방광암 (pTis, pT1)과 4기를 제외한 갑상샘암은 허용된다. 갑상샘암의 경우 수술적인 제거가 되지 않았더라도 연구자의 판단 하에, 전이성 대장암의 치료 경과와 예후에 영향을 주지 않는다는 연구자의 판단이 있다면, 총 책임 연구자와 상의 후 환자를 연구에 참여시킬 수 있다.
 
11. 조절되지 않은 중추신경계 전이.
 
12. 이전의 방사선 치료 병력은 허용된다. 그러나 방사선 조사 범위에 들어가지 않는 평가 가능 병변의 존재가 있어야 한다.
 
13. 원칙적으로 연구 치료 기간 동안의 방사선 치료는 허용되지 않는다. 그러나 연구자가 질병진행의 증거가 없는 치료병변 외의 부위에 방사선 치료가 필요하다고 판단되는 경우 총 책임연구자와 상의 후 진행 할 수 있다.
 
14. New York Heart Association (NYHA) class 2 이상의 심부전.
 
15. 3개월 이내의 불안정성 협심증 병력, 또는 최근의 새로 생긴 심근 허혈 증상, 또는 6개월 이내의 심근 경색 병력이 있는 경우.
 
16. 2년 이내의 활동성 자가면역질환, 단 전신 치료가 필요하지 않는 vitiligo, 그레이브스씨 병, 건선은 허용된다.

	
 17. 염증성 장질환의 병력 18. 면역억제의 병력 19. 장기 이식 환자 20. Durvalumab 또는 비슷한 약제에 대한 과민반응 21. 연구 참여 시 활동성 결핵이 있는 경우 22. 생백신 (live attenuated vaccine) 투여 후 30일 이내 23. HIV 감염 병력 또는 알려진 면역결핍 синдром. 24. 스크리닝 단계에서 활동성HBV/HCV 감염(HBV 표면항원양성 또는 HCV RNA 양성). 단, 회복된B형간염(anti HBs 와 anti HBc가확인되고, HBsAg, HBV DNA가 검출되지 않는 경우) 또는 HBsAg, HBV DNA로 확인된 만성 B형 간염의 경우 제외. 만성 B형 간염의 경우 항바이러스제 치료 중이며, HBV DNA <100IU/mL 임을 반드시 확인해야 한다. 25. 연구 시작 28일 이내의 주요 수술 또는 심각한 외상 병력. 26. 치유되지 않은 창상, 궤양 또는 골절. 27. 위장관 출혈이 지속되거나, 장 폐색이 의심되는 경우. 28. 현재 다른 약물이 투여되는 임상 연구에 참여 중인 경우. 29. 임신부 또는 모유 수유 중인 환자. 가임기의 여성은 연구 참여 7일 이내에 임신 반응 검사를 시행하여야 하며 음성임이 확인되어야 한다. 30. 연구 참여와 연구 결과 해석에 지장을 줄 수 있다고 판단되는 약물 남용자, 내과적/정신과적/사회적 질환을 가진 자.

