7.7. CONCOMITANT THERAPY

7.7.1. PROHIBITED CONCOMITANT MEDICATIONS

- Any investigational anticancer therapy other than those under investigation in this study.
- Any concurrent chemotherapy, immunotherapy or biologic or hormonal therapy for cancer treatment.
- Any concurrent radiotherapy is not permitted; however, if the local investigator decides that radiation therapy should be given during study treatments, he should be convinced that there is no evidence of disease progression and there is no target lesion(s) included in the field of radiotherapy with agreement of the chief principal investigator.
- Immunosuppressive medications including, but not limited to, systemic corticosteroids at doses exceeding 10 mg/day of prednisone or equivalent, methotrexate, azathioprine, and tumor necrosis factor- α blockers.
- Live attenuated vaccines are not permitted; inactivated vaccines (i.e. influenza vaccines) are permitted.
- Drugs with laxative properties and herbal or natural remedies for constipation.
- Prophylactic administration of G-CSF (or GM-CSF) or erythropoietin.
- All traditional medicines with an intention to control the tumor without regard to their truth

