8.2. EVALUATION BEFORE STUDY TREATMENT (WITHIN 2 WEEKS)

- Complete medical history.
- Physical examination including ECOG performance status.
- Radiologic assessments using RECIST 1.1. (permitted to be assessed within 28 days from the study treatment)
- CBC with differentials.
- Serum chemistry: calcium, phosphorus, glucose, BUN, creatinine, total protein, albumin, AST/ALT, alkaline phosphatase, total bilirubin, uric acid and electrolytes.
- Routine urinalysis
- Serum CEA
- Serum TSH, T3 and free T4
- Serum amylase/lipase
- EKG (3 consecutive EKG for eligibility check)
- Chest X-rays
- Urine β -hCG will be performed in women with child-bearing potential.
- Other tests (i.e. bone scans) if clinically indicated
- Exploratory biomarker assessments:
 - Opal Multiplex Tissue Staining with Opal™ including PD-1 and PD-L1
- Biological samples will be obtained for biomarker evaluation from all eligible patients at the screening visit.

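### Exclusion 12 asks only for an evaluable non-irradiated lesion and nothing ties the baseline scan to pre-dose radiotherapy, so radiation shrinkage could count as a durvalumab response

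*Combined protocol and SAP*

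**What the plan says.** **Prior radiotherapy.** Section 6.1.2, exclusion 12: "Prior radiation therapy would be permitted, but non-irradiated evaluable lesions should be present at study entry". The English synopsis has the same criterion in nearly the same words. Section 6.1.1, inclusion 4, asks for one or more "measurable lesion(s) by RECIST 1.1" and does not mention irradiation.

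**Intervals before the first dose.** Exclusion 3 is limited to chemotherapy: "Receipt of the last dose of chemotherapy ≤ 28 days prior to the first dose of study drugs". Exclusion 25 sets 28 days for major surgery or significant trauma. No criterion sets an interval for radiotherapy.

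**Baseline scan.** Section 8.2 and the synopsis exempt imaging from the two-week screening window; it is "permitted to be assessed within 28 days from the study treatment". Nothing links its date to radiotherapy.

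**Radiotherapy during treatment.** English exclusion 13 allows an exception in which the local investigator decides that radiotherapy is needed: "he should be convinced that there is no evidence of disease progression with agreement of the chief principal investigator". Section 7.7.1 allows the same exception but adds that "there is no target lesion(s) included in the field of radiotherapy". Exclusion 13 in the Korean synopsis also limits the site: "치료병변 외의 부위에 방사선 치료가 필요하다고 판단되는 경우", that is, radiotherapy judged necessary at a site other than the treated lesion.

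**Endpoint and rule.** The primary endpoint is objective response by RECIST 1.1 (section 4.1). Section 10.2 sets a Simon two-stage design: continue with 2 or more responses in 10 patients, and declare the treatment effective with 6 or more in 29.

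**The concern.** A response counts for durvalumab only if durvalumab is the credible cause of the shrinkage. Exclusion 12 appears meant to secure that, but it asks for a lesion that is evaluable, while response is judged on lesions that are measurable. An irradiated measurable lesion and a separate non-irradiated, non-measurable one together satisfy both criteria.

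Timing makes this worse. Radiotherapy can fall between the baseline scan and the first dose without breaching any written criterion. The lesion is then measured before irradiation and again at week 8, and shrinkage from either cause is read as response.

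With no control arm, nothing in the trial would reveal radiation effect. The error runs one way, because radiation shrinkage can only add apparent responses, and the decision turns on small counts.

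**Working it through.** **1. Does a patient with an irradiated sole target meet the criteria?** Take one measurable lesion, one small non-measurable lesion that is never irradiated, a baseline CT on day -28, radiotherapy to the measurable lesion between day -27 and day -1, and the first dose on day 1.

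| Criterion | Met on its text? |
|---|---|
| Inclusion 4: measurable lesion | Yes, on the day -28 scan |
| Exclusion 12: non-irradiated evaluable lesion | Yes, the small lesion |
| Exclusion 3: 28-day interval | Not engaged; chemotherapy only |
| Section 8.2: scan within 28 days | Yes |
| Exclusion 13 and section 7.7.1 | They address radiotherapy during study treatment or concurrent radiotherapy; neither clearly reaches the interval before dose 1 |

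The patient is eligible.

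**2. Two cases differ in weight.**
- *Radiotherapy finished before the baseline scan.* Shrinkage up to the scan is already in the baseline; only later shrinkage could be misattributed.
- *Radiotherapy between the scan and the first dose.* All of its effect falls after the baseline measurement. This is the strong case.

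**3. Reproduce the design.** Inputs from section 10.2: 10 then 19 patients; thresholds 2 and 6; rates 10% and 30%.

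P(success) = sum over x = 2 to 10 of P(X1 = x) × P(X2 ≥ 6 − x), with X1 ~ Bin(10, p) and X2 ~ Bin(19, p).

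- p = 0.10: 0.0471, within the stated 5%.
- p = 0.30: 0.805, matching the stated 0.8.
- 29 / 0.9 = 32.2, rounded up to 33.

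The stated design is correct.

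**4. Illustrate the effect of affected patients.** Assumptions, none from the documents: k of the 29 patients have an irradiated target; each has chance q of an apparent PR or CR; all other patients respond at 10%; affected patients fall at random across the two stages. If k1 of the k are in stage 1:

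- weight = C(10, k1) × C(19, k − k1) / C(29, k)
- X1 ~ Bin(10 − k1, 0.10) + Bin(k1, q), and X2 likewise with the remaining k − k1 patients.

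Worked for k = 1, q = 0.5. In stage 2 (weight 19/29 = 0.655), P(success) is 0.0680; in stage 1 (weight 10/29 = 0.345), it is 0.0833. The total is 0.655 × 0.0680 + 0.345 × 0.0833 = 0.073.

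| k | q | P(success), true drug rate 10% |
|---|---|---|
| 0 | – | 0.047 |
| 1 | 0.2 | 0.054 |
| 1 | 0.5 | 0.073 |
| 2 | 0.3 | 0.076 |
| 2 | 0.5 | 0.109 |
| 3 | 0.5 | 0.155 |

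A cruder version replaces everyone's rate by the average 0.10 + (k/29)(q − 0.10). At q = 0.5 this gives 0.078, 0.118 and 0.167 for k = 1, 2 and 3, slightly too high because it treats all 29 patients as alike.

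**The case against.** **RECIST 1.1 may already deal with this.** Measurability and response are both referred to RECIST 1.1, so a reader who infers that the trial definitely permits irradiated target lesions goes too far. Target selection is delegated to a standard that the documents do not reproduce, and whether it closes the gap cannot be settled from them. This objection limits the claim to the protocol's own text. It does not remove it: the protocol writes its own rule on irradiated lesions, that rule says evaluable, and the order of scan and radiotherapy is left open.

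**Evaluable may have been meant as measurable.** Section 8.4 and the synopsis join the two words with a slash, which can link near-synonyms, and the Korean pre-treatment checklist asks for measurable lesions to be confirmed. Against this, the Korean synopsis uses different words in inclusion 4 and exclusion 12. The intent is ambiguous, which is itself a reason to fix the wording.

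**The worked patient is unusual.** That is fair. It takes a single measurable lesion, irradiated in a short interval, plus a second lesion too small to measure. The documents give no frequency, so the probabilities above are illustrations.

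**On-study radiotherapy.** A reader of English exclusion 13 alone might infer that a target lesion may be irradiated during treatment. The documents do not support that. Section 7.7.1 binds the same sites and keeps target lesions out of the field, and the Korean item also limits the site. The mismatch is one of alignment and not a separate route to bias.

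**Conclusion.** The point holds as a gap in the written criteria for radiotherapy given before the first dose. Exclusion 12 does not require a non-irradiated measurable lesion, inclusion 4 does not supply that condition, and nothing places the baseline scan after radiotherapy. Radiation shrinkage could therefore enter the primary endpoint as response, most clearly when radiotherapy falls between the scan and the first dose.

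The size is unknown. One to three affected patients would move the false-success probability from 0.047 to somewhere between 0.054 (one patient, 20% chance) and 0.155 (three patients, 50% chance). Both the number and the chance are assumed. This does not show that the trial's type I error is inflated, nor that the sample size or decision rule is wrong; both reproduce. Any effect on disease control or PFS was not calculated. The change is worth making because the bias favours the drug, cannot be seen without a control arm, and is cheap to prevent.

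**What to change.** 1. In exclusion 12 (section 6.1.2 and both language versions of the synopsis), require at least one non-irradiated lesion that is measurable by RECIST 1.1.
2. State that target lesions are chosen only from non-irradiated lesions.
3. State that a lesion irradiated between its baseline measurement and the first dose may not serve as a target, or that the baseline scan must be taken after that radiotherapy.
4. Reconcile English exclusion 13, Korean exclusion 13 and section 7.7.1, so that the conditions on radiotherapy during treatment read the same everywhere. This is an alignment edit.

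If patients are already enrolled, identify at analysis any responder whose target lesion was irradiated before the first dose, with the date relative to the baseline scan, and show the response rate with and without those responses.

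**Cost.** A few patients whose only measurable lesion was irradiated become ineligible, and an occasional baseline scan is repeated. The 29 evaluable and 33 enrolled patients, the 2-of-10 and 6-of-29 rules and the type I error of 0.047 all stay as they are.
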